### 1.2 Standard Treatment

[figure not shown]
The current standard-of-care treatment for AH includes prednisolone, a corticosteroid which works by altering the balance of cytokines, reducing pro-inflammatory cytokines, e.g. tumour necrosis factor- $\alpha$  (TNF- $\alpha$ ), and increasing anti-inflammatory cytokines such as interleukin-10 (IL-10) (Saberi et al. 2016). However, prednisolone is of limited efficacy and has numerous side effects (Crabb et al. 2016); in the presence of infection, steroids are contraindicated (Sanyal & Gao. 2015) and is often replaced by pentoxyphilline. This and other treatments for severe AH have not consistently shown a survival benefit (Crabb et al. 2016).

Patients suffering with severe acute decompensated AH often present as malnourished. Nutritional supplementation is also provided as a primary treatment for AH and, in some studies, has been seen to facilitate equal, if not better, survival compared to treatment with corticosteroids (Morgan. 2007).

There is an obvious unmet need for advanced treatment in this life threatening indication.

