### **3 RATIONALE FOR THE STUDY**

The postulated mode of action of DS102 covering all relevant pathophysiological features of severe acute decompensated AH together with a preclinically and clinically clean safety profile of the compound makes DS102 an ideal candidate to evaluate clinically the effects of DS102 in this life threatening disease, for which no established treatment is available.

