### **10.2 Dosage and Administration**

Patients who fulfil all inclusion and no exclusion criteria may be accepted in the study. Each patient must read and sign an ICF prior to any screening procedures being performed. This study involves a comparison of DS102 with placebo, administered orally within 30 minutes after a meal twice daily for a total duration of 28 days. Patients will also receive standard of care therapy in addition to their assigned IMP throughout the treatment period of the study. The last study drug administration should occur on the day preceding Visit 6/Day 28/Early Termination.

[figure not shown]
Patients will be randomised to one of the two treatment groups in a 1:1 ratio:

- Treatment group A: 2 x placebo 500mg capsules orally administered BD (four capsules daily) for 28 days

- Treatment group B: 2 x DS102 500mg capsules orally administered BD (four capsules daily) for 28 days

Patients will be required to take the capsules within 30 minutes after a meal. Medication(s) for other conditions that are permitted in the study can be taken as usual.

Walleted blister packs will consist of seven days of four capsules. Patients will be instructed to take the two capsules **from left to right**, on the relevant day, as shown below:

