## 12 STATISTICAL METHODOLOGY AND DATA MANAGEMENT

### 12.1 Study Design

This clinical trial employs a randomised, double-blind, placebo-controlled 2-arm parallel group design preceded by an open-label pilot phase. Randomisation is used to minimise assignment bias and to increase the likelihood that known and unknown patient attributes (e.g. demographic characteristics) are evenly balanced across the treatment groups. Blinding is used to reduce potential bias during data collection and the evaluation of safety and efficacy. The use of placebo as a comparator is justified as a reasonable design to assess safety and efficacy in patients based on the brevity of the study duration and the absence of any real established standard of care for alcoholic hepatitis. A full description of the study design is presented in Section 6 above.

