### 12.2 Randomisation

For the open label pharmacokinetic pilot phase, six patients will be enrolled and treated with study drug (2 x DS102 500mg capsules orally administered BD (four capsules daily)), for 28 days. Results of this pilot phase will be assessed by a DSMB for safety and if dose adjustments for the main study are needed.

For the main, double-blind phase, approximately 120 patients will be randomised into double-blind treatment groups in a 1:1 ratio as follows:

- Treatment group A: 2 x placebo 500mg capsules orally administered BD (four capsules daily) for 28 days
- Treatment group B: 2 x DS102 500mg capsules orally administered BD (four capsules daily) for 28 days

At the investigational site, each patient will be assigned a patient screening number during screening that will be used on all patient documentation. The patient screening number will contain the site number and the patient number assigned in numerical order at the screening visit (e.g.: 02-010 for the tenth patient screened at the site #02). Numbers will be assigned in ascending order starting with 001.

A randomisation list, permuted blocks and stratified by site, will be generated by Afimmune or its designee. The randomisation schedule with study drug assignments will be generated prior to the start of the study and will be known only to the individuals responsible for labelling the study drug, the statisticians generating the schedule and the interactive web response system (IWRS) team responsible for implementing the schedule. The IWRS will assign medication kit numbers to each patient, as required, at visits and the contents will be based on the randomisation code.

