6.9 Prior and Concomitant Medications

Medications will be coded using the latest World Health Organization Drug dictionary (WHO Drug) version. The version used will be indicated in the data summaries and listings.

Prior medications are defined as those that started and ended prior to the first administration of study treatment. Medications that are ongoing at the first administration of study treatment or started after time of first administration will be deemed to be concomitant medications. If medication dates are incomplete and it is not clear whether the medication was concomitant, it will be assumed to be concomitant.

The number and percentage of patients taking prior and separately concomitant medications will be summarised by medication class and standardised medication name, where medication class and standardised medication name will be presented in decreasing frequency of the total number of patients with medications. In summary tables, patients taking multiple medications in the same medication class or having the same standardised medication recorded multiple times in the study will be counted only once for that specific medication class and standardised medication name.

Medication data will be listed, and concomitant medications will be flagged.

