6.11.1 Primary Analysis

Percentage change in MELD score from baseline up to and including day 28 will be assessed by modelling change from baseline with a mixed-model repeated measures (MMRM) analysis, using the FAS, including terms for treatment group, visit, treatment-by-visit interaction as fixed effects and the baseline MELD value as a covariate. The adjusted treatment least squares (LS) means and adjusted mean LS difference between the active dose and placebo will be presented along with 95% confidence intervals (CI) and p-value for the day 28 timepoint. Early termination data will be entered into the model at the next scheduled visit following the date of termination, not at day 28.

F-tests from PROC MIXED will be based on Kenward-Roger's adjusted degrees of freedom. The following variance/covariance matrix structures for the repeated visits within a patient will be assessed: Compound symmetry, 1st order autoregressive, Toeplitz and unstructured. The variance/covariance matrix structure that results in the smallest Akaike's information criterion (AIC), indicating the best model fit will be selected.

Assumptions of normality will be assessed visually using diagnostic plots. Should assumptions of normality not hold the model will be fitted to the change from baseline of log-transformed data. Should the assumptions behind the model still not hold an alternative approach to the analysis will be decided following the BDRM and will be detailed in a SAP amendment.

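### Background steroid use at first dose will differ between patients, but it is neither a stratification factor nor a covariate in the primary MELD model: a modest loss of precision that is cheap to recover

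*Protocol*

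**What the plan says.** **Background treatment.** Protocol 1.2: "The current standard-of-care treatment for AH includes prednisolone, a corticosteroid which works by altering the balance of cytokines". The same paragraph calls prednisolone of limited efficacy and says that "in the presence of infection, steroids are contraindicated". Protocol 10.2: "Patients will also receive standard of care therapy in addition to their assigned IMP throughout the treatment period of the study". Section 6.1 and SAP 2.3 say the same. None of them fixes or defines steroid use.

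**Placebo justification.** Protocol 12.1 rests the choice of placebo partly on "the absence of any real established standard of care for alcoholic hepatitis". Section 3 describes the disease as one "for which no established treatment is available".

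**Allocation.** Protocol 12.2: "A randomisation list, permuted blocks and stratified by site, will be generated by Afimmune or its designee". SAP 2.3 gives 50 sites in 9 countries.

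**Primary model.** SAP 6.11.1 specifies an MMRM "including terms for treatment group, visit, treatment-by-visit interaction as fixed effects and the baseline MELD value as a covariate". Protocol 12.8.2 has the same terms. The sensitivity analyses in SAP 6.11.2 are the per-protocol set and last observation carried forward.

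**Medication tables.** SAP 6.9: "Medications that are ongoing at the first administration of study treatment or started after time of first administration will be deemed to be concomitant medications". All medication data are also listed, and the section's rule for incomplete dates shows that dates are recorded.

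**The concern.** Some patients will be on a steroid at first dose and others not. By the protocol's own account infection is one reason, and with 50 sites in 9 countries and no defined regimen, local practice is likely to be another. Screening lasts up to five days from admission, so the timing of a steroid start relative to first dose will also vary.

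If steroid status at entry predicts the MELD course to Day 28, leaving it out of the model costs precision. It also lets any chance difference between the arms pass into the Day 28 contrast. Baseline MELD does not cover this, because it cannot capture the later response to a steroid. No planned table shows whether the arms were balanced at first dose. If an imbalance is noticed only after unblinding, a covariate added then carries little weight. Prespecification is therefore what is at stake.

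**Working it through.** **Inputs from the documents.** Effect size 0.54 SD, two-sided alpha 0.05, 80% power, 55 per group needed and 60 randomised (protocol 12.3, SAP 3). Fifty sites (SAP 2.3).

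**Inputs assumed.** The share on a steroid at first dose, *p*, is 0.3 to 0.7. The Day 28 MELD difference between steroid and non-steroid patients, *g*, is 0.3 to 0.5 SD net of baseline MELD. The documents give neither, so *g* = 0.2 and zero are shown as well. All 60 per arm are taken as observed at Day 28.

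**1. The plan's own figure.** Two-sample t-test power from the noncentral t distribution with d = 0.54 is 0.7940 at 54 per group and 0.8014 at 55. The stated 55 reproduces and is not in question. At 60 per group the power is 0.835.

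**2. Chance imbalance.** The SD of the between-arm difference in steroid share is √(2p(1−p)/60).
- *p* = 0.3 or 0.7: √(0.42/60) = 0.084. The 95% limit is 1.96 × 0.0837 = 0.164.
- *p* = 0.5: √(0.50/60) = 0.091. The 95% limit is 1.96 × 0.0913 = 0.179.

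An imbalance of 10 points or more has probability 0.23 to 0.27. Site stratification is given no credit here. At 120/50 = 2.4 patients per site on average, most blocks are likely to be incomplete, so its help is partial.

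**3. Shift in the contrast** (imbalance × *g*, at the 95% limit).

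| *g* (SD) | *p* = 0.3 or 0.7 | *p* = 0.5 | Share of 0.54 |
|---|---|---|---|
| 0 | 0 | 0 | 0% |
| 0.2 | 0.033 | 0.036 | 6–7% |
| 0.3 | 0.049 | 0.054 | 9–10% |
| 0.5 | 0.082 | 0.089 | 15–17% |

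At an imbalance of one SD, the shift for *g* = 0.3 to 0.5 is 0.084 × 0.3 = 0.025 to 0.091 × 0.5 = 0.046 SD.

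**4. Type I error.** Simulation of 50,000 trials per setting at 50% use, with the steroid term omitted, gave overall rejection rates of 0.048 (*g* = 0.3) and 0.049 (*g* = 0.5). The mean treatment difference was −0.001 SD in both. Among simulated trials with an imbalance of at least 15 points, which has probability about 0.10, the rates were 0.058 and 0.066.

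**5. Power.** The residual SD after adjustment is √(1 − p(1−p)g²). At *p* = 0.5:
- *g* = 0.2: variance explained 0.010, residual SD 0.995, effect 0.54/0.995 = 0.543, power 0.839.
- *g* = 0.3: variance explained 0.0225, residual SD 0.989, effect 0.54/0.989 = 0.546, power 0.843.
- *g* = 0.5: variance explained 0.0625, residual SD 0.968, effect 0.54/0.968 = 0.558, power 0.858.

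**6. Is one steroid term enough?** Suppose all six scheduled post-baseline visits (Days 3, 5, 7, 14, 21, 28) enter the model and the steroid effect grows in proportion to time (an assumption). A single main effect then estimates an average over visits. Under compound symmetry this is (3+5+7+14+21+28)/6 = 13 days' worth, or 13/28 = 46% of the Day 28 effect. Under first-order autoregression with correlation 0.6 to 0.8 it is 49–52%. About half of the Day 28 shift would remain, so the term must be allowed to vary by visit.

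**The case against.** The strongest reply is that this is ordinary chance variation. Steroid status at first dose precedes any treatment effect, and the confidence interval already allows for imbalance in it. The same could be said of any unmodelled prognostic factor in an exploratory phase II trial. That stands. A reader might infer that the primary result is biased or its type I error inflated. The documents do not support that: allocation is randomised, and step 4 shows an overall error near 5%.

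The size is assumed, and the only evidence in the documents on efficacy points down, since section 1.2 calls prednisolone of limited efficacy. This also stands. At zero effect there is nothing to correct.

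A reader might also infer that baseline balance on steroids could never be established. It could, because medication is assessed at screening and baseline and SAP 6.9 lists it all. Only the tables pool it.

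Nor do the documents support reading 12.1 as placebo in place of background care. That section refers to section 6, where standard of care is given to both arms, and the phrase can be taken to mean that no effective standard exists. What remains is a tension in wording.

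Untreated or unresolved sepsis is excluded, which narrows the infection-driven split in prognosis but does not close it, because treated infection may enter. Patients who start a steroid shortly after first dose would be coded as non-users, so the flag partly records timing. That limits the gain but does not invalidate the adjustment.

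**Conclusion.** The point holds as one of precision and credibility, not validity. Steroid use at first dose is a plausible prognostic factor that the plan lets vary between patients, and nothing in the randomisation beyond site, or in the primary model, takes it up. Under 30–70% use and a 0.3–0.5 SD effect, both assumed, an imbalance at its 95% limit would move the contrast by 0.05–0.09 SD, or 9–17% of the planned 0.54. At 50% use, adjustment lifts power at 60 per arm from about 0.835 to 0.843–0.858. The sample size is correct and does not need to rise. The gain is modest and shrinks with a smaller steroid effect, but it comes from data already collected and is worth prespecifying before unblinding.

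**What to change.** 1. In the SAP, derive a yes/no flag for systemic corticosteroid ongoing at first dose from the dated medication records. State how incomplete start dates and starts on the day of first dose are classified.
2. Add the flag and its interaction with visit to the SAP 6.11.1 model. With six post-baseline visits this costs 1 + 5 = 6 fixed-effect parameters, affordable with 120 patients.
3. State that steroids started after first dose are not adjusted for, since treatment may influence them.
4. In SAP 6.9, tabulate by arm steroids ongoing at first dose separately from those started afterwards.
5. As a minor wording change, reconcile protocol 12.1 and section 3 with 1.2 and 6.1, so that all four describe the same background treatment.

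The cost is SAP text, one derived variable, one extra table and the wording correction. No new data are needed, and patient care does not change.

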### 1.3 Drug Class

DS102 is an endogenously occurring fatty acid 15-hydroxy-eicosapentaenoic acid ethyl ester (15-HEPE EE).

**Figure 1. Structure of 15(S)-HEPE EE (DS102)**

#### 1.4 Preclinical Pharmacology

A number of *in vitro* and *in vivo* mechanistic studies were performed by the company to elucidate the pharmacology of DS102 (DS-PC-17, DS-PC-18, DS-PC-21, DS-PC-22, DS-PC-23, DS-PC-26, DS-PC-27, DS-PC-28, DS-PC-29, and DS-PC-32).

DS102 has been shown (Table 1) to be significantly anti-apoptotic in a staurosporin model of apoptosis. The anti-inflammatory effects of DS102 were illustrated in a model of lipopolysaccharide (LPS) induced inflammation in peripheral blood mononuclear cells (PBMCs) showing a significant decrease in tumour necrosis factor- $\alpha$  (TNF- $\alpha$ ), IL-6, IL-8 and IL-23. Anti-fibrotic effects of DS102 were observed in TGF- $\beta$  treated fibroblasts isolated from idiopathic pulmonary fibrosis (IPF) patients, reducing the production of fibrotic markers collagen and  $\alpha$ -smooth muscle actin ( $\alpha$ -SMA). DS102 also showed varying degrees of peroxisome proliferator-activated receptor (PPAR) activation in human PPAR reporter cells. DS102 has therefore been shown to have a pleiotropic mechanism of action including key anti-inflammatory and anti-fibrotic mechanisms involved in the pathogenesis of AH.

**Table 1: DS102 Mechanism of Action Summary**

#	Type	Model	Objective	Result
1.	In vivo	Tissue Distribution Study	Rats dosed for 7 days with DS102 and tissues levels assessed	DS102 was sequestered in, but not exclusively to, the liver, lung, heart, spleen and kidney tissues.
2.	In vivo	Whole genome screen of rat genome	Rats Dosed for 4 days with DS102 and genome array performed	Increases in cell proliferation markers (e.g. cyclins), hepatoprotective cytokines (IL-11) and fatty metabolism receptors.
3	In vitro	TGF-beta Induced Fibrotic Markers	DS102 anti-fibrotic properties	DS102 inhibited TGF-beta induced collagen and alpha-SMA (Smooth Muscle Actin)
4.	In vitro	LPS induced Inflammation	DS102 anti-inflammatory properties	DS102 inhibited TNF-alpha, IL-6, IL-8 and IL-23
5.	In vitro	Screening of PPAR family in Human PPAR reporter cells	Investigate the mechanism of action for DS102 via the PPAR family signalling pathway	DS102 moderately activated PPAR-alpha and mildly activated delta and gamma
6.	In vitro	Staurosporine induced Caspase Activity	To investigate the Caspase 3 inhibition potential of DS102	DS102 showed to be a potent caspase inhibitor in response to staurosporine induced cell death

Investigation of DS102 in the pathological progression of non-alcoholic steatohepatitis (NASH) was performed in an established NASH preclinical model (STAM™) sponsored by the company. As

[figure not shown]
---

it is postulated that pathophysiologically AH is in principle an accelerated form of NASH, it can be

assumed that results from this study can also be used to expand upon knowledge of DS102 in the pathological progression of AH.

**A subcutaneous injection of streptozotocin was administered to newborn mice followed by a high fat diet from four weeks of age. Results presented below represent overall outcomes from four studies performed. NAS score (NAFLD Activity Score) is separated into three components: steatosis, lobular inflammation and hepatocyte ballooning. Light arrows signify a decrease. Dark arrows signify a statistically significant difference in the extent of decrease.**

**Figure 2: Schematic summarising the results of four *in vivo* studies performed using the STAM™ Model (DS-PC-26, DS-PC-27, DS-PC-28, and DS-PC-29).**

Treatment with DS102 at 500mg/kg significantly decreased plasma ALT, a liver injury marker, and plasma TGF-β, a marker of fibrosis progression. Histological analysis showed DS102 also significantly decrease NAFLD activity score (NAS). The improvement of NAS was attributable to the reduction in the lobular inflammation and hepatocellular ballooning scores. It also showed its efficacy in liver fibrosis of STAM™ mice. The treatment reduced the pathological deposition of collagen (perisinusoidal fibrosis) in the liver as demonstrated by Sirius red staining.

The above results suggest that DS102 has potential hepatoprotective and anti-inflammatory effects against steatohepatitis. Recent research has linked fibrosis, as well as bilirubinostasis, with a poor outcome of AH (Sanyal & Gao. 2015). The reduction of fibrosis area suggests that DS102 treatment could contribute to achieve a better prognosis in AH.

The *in vitro* and *in vivo* studies performed to date illustrate the hepatoprotective, anti-inflammatory and anti-fibrotic mechanisms of DS102 and supports its development as a compound to treat AH.

## 1.5 Toxicology

A number of good laboratory practice (GLP) toxicology studies were performed by the company to assess the safety of DS102 (CRL-527943, 527959, 529139, 529123). Daily administration of DS102 up to 2000mg/kg/day for four weeks to rats and dogs was deemed well tolerated and safe. The no observed adverse effects levels (NOAEL) for repeated dosing over four weeks in both species was 2000 mg/kg/day. The company recently completed a nine month dog and six month rat study; both studies concluded that administration of DS102 was well-tolerated with a NOAEL of 1000mg/kg/day.

## 1.6 Previous Clinical Safety Studies with 15(S)-HEPE

The company sponsored a phase I study, DS102A-01 (EudraCT 2015-001153-33), a first in man study conducted in healthy volunteers, to assess the safety, pharmacokinetics and effect of food on orally administered DS102. DS102 (15(S)-HEPE EE) was administered to healthy volunteers in the following regimens: a single dose of 100mg, 500mg, 1000mg, or 2000mg under fasted conditions; a single 500mg dose under two fed conditions (standard diet and high fat diet); and as multiple doses of 500mg, 1000mg or 2000mg taken once daily for 28 consecutive days in a fasted state. In this study, 57 subjects (male and female) aged 18 to 45 years were enrolled with eight subjects (at least three males and three females per cohort) in each cohort. Subjects in each cohort were randomised in a ratio of 3:1 to receive either DS102 or placebo. Cohorts were commenced in a sequential manner starting with the 100mg, 500mg and 1000mg single dose cohorts in parallel and progressing to higher doses and multiple doses following evaluation by a safety monitoring committee (SMC).

This first in man study showed that DS102 overall had an excellent safety profile, a short elimination half-life of approximately two hours and a  $T_{max}$  of approximately four to eight hours. Results across dose levels studied showed high variability in the single and multiple dose cohorts and did not show a linear correlation between increasing dose and that of systemic exposure. The study demonstrated that administration with food increased the bioavailability of 15(S)-HEPE, as mean plasma concentrations of 15(S)-HEPE were higher under fed conditions compared to fasted conditions. There was no difference in bioavailability between normal and high fat diet fed conditions. DS102 was safe and well-tolerated in healthy subjects in this study with no serious adverse events (SAEs) reported.

The company is currently recruiting patients for two phase II studies, DS102A-02 (EudraCT 2016-000311-33), to assess the safety and efficacy of orally administered DS102 in NAFLD patients at doses of 1000mg or 2000mg per day, with placebo as a comparator and DS102A-03 (EudraCT 2016-002853-39), to assess the safety and efficacy of orally administered DS102 in COPD patients at doses of 1000mg or 2000mg per day, with placebo as a comparator. To date, DS102 has been well-tolerated with no related SAEs reported.

